## **4.7 Exposure to Treatment**

### **4.7.1 Extent of ADCT-301 Exposure**

ADCT-301 exposure will be summarized for the safety analysis set by dose level. Duration of treatment, total number of cycles dosed, total dose received (in  $\mu\text{g}$  and  $\mu\text{g}/\text{kg}$ ), and average dose per cycle (in  $\mu\text{g}$  and  $\mu\text{g}/\text{kg}$ ) will be tabulated. When actual weight adjusted dose is needed, the last available weight before each infusion will be used. Dose administered at each infusion ( $\mu\text{g}$ ) is calculated by concentrated IP volume (in mL)\* 6 mg/mL \*1000 or serially diluted IP volume (in mL)/50\* 6 mg/mL \*1000; for partial infusion, multiply by (1-volume of dosing solution not administered [in mL]/ 50 mL).

Dose delays and dose reductions could also be analyzed if relevant. A cycle is delayed if it starts more than 2 days post- scheduled date.

Exposure data and infusion details will be listed together.

### **4.7.2 Prophylactic Medications for Hypersensitivity**

Prophylactic medications for hypersensitivity will be listed only.

### **4.7.3 Subsequent Anticancer Therapy or Procedure**

Patients' subsequent anticancer therapies or procedures including systemic therapy, radiation, transplant, or other, along with the start date of new anticancer therapy or procedure will be collected and listed only.

## 4.8 Safety Analyses

The summary of safety results will be presented by treatment group.

### General common rules

All safety analyses will be performed on the safety analysis set, unless otherwise specified, using the following common rules:

- The baseline value is defined as the last non-missing value or measurement taken up to the first dose in the study.
- The analyses of the safety variables will be essentially descriptive and no systematic testing is planned.
- If relevant, selected safety analyses will be summarized by age, sex, racial subgroups, and any pertinent subgroups.
- The toxicity grade according to the Common Terminology Criteria for Adverse Events (CTCAE) version 4.0 will be taken into account in the summary. For patients with multiple occurrences of the same event, the maximum grade is used. If a patient has both missing and non-missing severity grades for treatment-emergent adverse events (TEAEs) within the same preferred term (PT), the patient will be counted under the non-missing severity grade.

### 4.8.1 Dose-limiting Toxicities (Part 1)

DLT data will be tabulated for the DLT-evaluable analysis set by dose group and type of DLT for Part 1 of the study. The patients enrolled prior to and post protocol amendment 4 will be presented in separate tables.

DLT data will be listed for Part 1 of the study.

### 4.8.2 Adverse Events, Serious Adverse Events, and Deaths

#### 4.8.2.1 Analyses of adverse events

The primary focus of adverse event reporting will be on TEAEs. An adverse event (AE) will be considered to be a TEAE if it begins or worsens on or after first dose date and until 84 days (12 weeks) after the last dose date, or start of a new anticancer therapy/procedure, whichever comes earlier.

An AE occurring before the first dose or more than 84 days (12 weeks) after last dose date or after the start of a new anticancer therapy/procedure will not be included in TEAE displays, but will be listed as non-TEAEs.

If an AE date/time of onset (occurrence, worsening, or becoming serious) is incomplete, an imputation algorithm will be used to classify the AE as pre-treatment, TEAE, or post-treatment. The algorithm for imputing date/time of onset will be conservative and will classify an AE as a treatment-emergent unless there is definitive information to determine it is a non-TEAE (pre- or post-treatment).

Details on classification of AEs with missing or partial onset dates are provided in Section 6.

### **Analysis of all TEAE(s):**

The following TEAE summaries will be generated for the safety analysis set in each dose level.

- Overview of TEAEs, summarizing number of TEAE and number (%) of patients with any
  - TEAE
  - Related TEAE (including possibly related, probably related, or related)
  - Any TEAE  $\geq$ Grade 3
  - Serious TEAE
  - TEAE leading to death
  - TEAE leading to permanent treatment withdrawal
  - TEAE leading to ADCT-301 delay or reduction or interruption
  - TEAE with at least one infusion related reaction
- All TEAEs by PT, showing number (%) of patients with at least one TEAE, sorted by decreasing incidence of PTs
- All TEAEs  $\geq$ Grade 3 by PT, showing number (%) of patients with at least one TEAE, sorted by decreasing incidence of PTs
- All TEAEs by primary System Organ Class (SOC) and PT, showing number (%) of patients with at least one TEAE, sorted by SOC in alphabetic agreed order and decreasing incidence of PTs within SOC. This sorting order will be applied to all other tables, unless otherwise specified.
- All TEAEs by primary SOC, PT and Maximal CTCAE grade, showing number (%) of patients with at least one TEAE, sorted by SOC and PT in alphabetic order. This sorting order will be applied to all other tables, unless otherwise specified.
- All TEAEs  $\geq$ Grade 3 by primary SOC, PT and Maximal CTCAE grade
- All related TEAEs by primary SOC, PT and Maximal CTCAE grade (including possibly related, probably related, or related)
- All TEAEs leading to treatment withdrawal by primary SOC, PT and Maximal CTCAE grade
- All TEAEs leading to dose delay by primary SOC, PT and Maximal CTCAE grade
- All TEAEs leading to dose reduction by primary SOC, PT and Maximal CTCAE grade
- All TEAEs leading to infusion interruption by primary SOC, PT and Maximal CTCAE grade
- All TEAEs with fatal outcome by primary SOC, PT and Maximal CTCAE grade
- All Serious TEAEs by primary SOC, PT and Maximal CTCAE grade

- All infusion related reaction TEAEs by primary SOC, PT and Maximal CTCAE grade
- Summary of grouped TEAEs selected by Standardised MedDRA Query (SMQ), ADCT modified SMQ will also be provided by Grouped PT term, and Maximal CTCAE grade. These group terms include: for effusion/edema, hepatic, fatigue, skin/nail, pain.
- Summary of common TEAEs will also be provided by demographic factors including: sex, age group, race, disease subtype if appropriate.

All TEAEs, all serious adverse events (SAEs), all TEAEs leading to treatment withdrawal, all TEAEs leading to dose reduction, all TEAEs leading to dose delay, all TEAEs leading to infusion interruption, all TEAEs considered infusion related reactions, all TEAEs with fatal outcome and non-TEAEs will be listed.

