4.1 Study Design

This is a Phase 1, FIH, open-label, dose-escalation (Part 1) and expansion (Part 2) study of ADCT-301 in patients with relapsed and refractory lymphoma. The study will evaluate the safety and tolerability of ADCT-301 as monotherapy, as well as the preliminary activity, PK, pharmacodynamics, and formation of ADAs of ADCT-301 in patients.

For each patient, the study will include a screening period (up to 28 days), a treatment period (until progressive disease, intolerable toxicity, or withdrawal of consent), and a follow-up period to assess disease progression and survival for up to 12 months after the last dose of study drug. The total study duration will be dependent on overall patient tolerability to the study drug and response to treatment. It is anticipated that the entire study (Parts 1 and 2) could last approximately 3 years from first patient treated to last patient completed.

In Part 1, patients will receive ADCT-301 administered as a 1-hour IV infusion on Day 1 of each 3-week (21-day) cycle. If ADCT-301 is well tolerated after the first cycle, the infusion duration may be shortened to 30 minutes for subsequent cycles at the Investigator's discretion.

The first patient at each dose level will be monitored for any AEs for 7 days before proceeding with dosing for the second patient.

The initial dose level for Part 1 will be 3 µg/kg (Dose Level 1). The highest allowed dose will be 300 µg/kg. The MTD will be the highest safe dose that has at least a 60% probability that the dose-limiting toxicity (DLT) rate is < 30%.

After discontinuation of treatment, patients without documented objective disease progression will be followed until progression of disease or initiation of new anticancer therapy for up to 12 months. All patients will be followed for survival (by telephone contact or retrospective chart review) until a new anticancer therapy is initiated or for up to 12 months after treatment discontinuation.

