8.3 Sample Size Calculations

This is a Phase 1 study with a total sample size of approximately 140 patients. It is expected that Part 1 will enroll approximately 80 patients, and Part 2 will enroll approximately 60 patients ([Section 4.1.1](#) and [Section 4.1.2](#)).

Simulations were performed assuming scenarios with different dose-toxicity relationships to evaluate the sample size for Part 1.

Patients will be enrolled in Part 2 of the study in cohorts of approximately 10. The cohorts will be enrolled at the dose level recommended in Part 1.

The DESC will make recommendations with regard to the intended differences between these cohorts, e.g. tumor subtypes, dosing regimen or dose levels, as well as the number of these cohorts, taking into account the limit on the overall number of patients as specified above and safety/efficacy data observed up to that decision point.

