## 4 Statistical methods

All analyses use SAS® version 9.4 or higher. Summary tables will be organized by each dose level; if some dose levels have few patients, then dose levels could be combined into dose ranges. All available data will be used in the analyses, and important data will be included in data listings, sorted by dose level, patient, and by visit within patient. Missing data will not be imputed, except via censoring in survival analyses and as otherwise specified.

Unless otherwise noted, categorical data will be presented using counts and percentages, with the number of patients in the analysis set by treatment group as the denominator for percentages. Percentages will be rounded to one decimal place, except 100% will be displayed without any decimal places and percentages will not be displayed for zero counts. Continuous data, unless otherwise noted, will be summarized using the number of observations (n), mean, standard deviation (std), median, minimum, and maximum. Minima and maxima will be rounded to the precision of the original value, and means, medians, and 95% confidence intervals (CIs) if presented will be rounded to 1 decimal place greater than the precision of the original value. The std will be rounded to 2 decimal places greater than the precision of the original value, up to a maximum of 3 decimal places.

No hypothesis testing will be performed in this study.

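### TEAE incidence by dose level is planned only as crude patient percentages over unequal observation windows, with no common-window or exposure-aware companion

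*SAP*

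**What the plan says.** SAP 4.8.2.1 introduces its list of tables with "The following TEAE summaries will be generated for the safety analysis set in each dose level". The tables give the number and percentage of patients with at least one event. The overview also gives a raw count of TEAEs. SAP 4 makes the number of patients in the analysis set the denominator and allows sparse dose levels to be pooled into ranges.

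An event counts as treatment-emergent when it "begins or worsens on or after first dose date and until 84 days (12 weeks) after the last dose date". The window closes sooner if the patient moves to another anticancer treatment before that date. Protocol 4.1 defines "a treatment period (until progressive disease, intolerable toxicity, or withdrawal of consent", with no fixed number of cycles.

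Exposure is tabulated separately by dose level in SAP 4.7.1 ("Duration of treatment, total number of cycles dosed, total dose received"), and nothing links that table to TEAE incidence. Neither document plans an exposure-adjusted rate, a time-to-onset analysis or a fixed-window table for TEAEs. DLTs are handled apart: SAP 4.1.2 and 4.8.1 tabulate them in a set defined by completed cycles. SAP 4 adds that "No hypothesis testing will be performed in this study".

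**The concern.** The length of the TEAE window depends partly on efficacy. A patient who progresses at the first scan leaves the window early; a patient who benefits stays in it. Columns of crude percentages set side by side then combine how often events occur per unit of time with how long patients were watched. The same applies to the planned summary of common TEAEs by disease subtype, because time to progression may differ between subtypes.

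Safety and tolerability is a primary objective in both parts, and SAP 4.8.2.1 makes TEAEs the main focus of adverse event reporting. For the secondary endpoints DOR, PFS and OS the SAP deals with unequal follow-up by Kaplan-Meier methods, but it does nothing comparable for adverse events. If Part 2 regimens are tabulated as groups, there is a further difficulty. The four candidates in Protocol 4.1.2 are identical through Cycle 3, so patients who stop before they diverge say nothing about the difference between them yet stay in the denominator.

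**Working it through.** The documents give no TEAE rate or expected exposure, so there is no planned figure to reproduce. The windows follow from the schedule; the hazards and the group mixes below are assumptions.

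**Windows.** Cycles last 21 days (Protocol 6.1). With k doses given on time, the last dose falls on Day 1 + 21(k − 1), and the window closes at the latest 84 days later. Scans fall at the end of Cycles 2, 4 and 7 (Protocol 7.1).

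- Stops at the first scan, k = 2: last dose Day 22, window to Day 106.
- Stops at the third scan, k = 7: last dose Day 127, window to Day 211.

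**Upper-end contrast.** Every patient in one group has 2 doses, every patient in the other has 7, both have the full 84-day tail, and the hazard is the same in both. It is scaled to give 30% by Day 211, so the cumulative hazard to Day 211 is −ln(0.7) = 0.3567. Let the hazard in the first 42 days be r times the later hazard. The share of cumulative hazard reached by Day 106 is (42r + 64)/(42r + 169), and the incidence by Day 106 is 1 − exp(−0.3567 × share).

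| r | Share by Day 106 | Incidence by Day 106 | Incidence by Day 211 |
|---|---|---|---|
| 1 | 106/211 | 16.4% | 30% |
| 3 | 190/295 | 20.5% | 30% |
| 10 | 484/589 | 25.4% | 30% |

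If new therapy closes the short window on Day 57 (assumed) and r = 1, the figure is 1 − exp(−0.3567 × 57/211) = 9.2%.

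**Mixed groups.** Real dose levels contain both kinds of patient. Assume 70% with 2 doses and 30% with 7 in one group, and 40% and 60% in the other. The gap is 0.3 × (30 − incidence by Day 106):

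- r = 1: 0.3 × 13.6 = 4.1 points
- r = 3: 0.3 × 9.5 = 2.8 points
- r = 10: 0.3 × 4.6 = 1.4 points

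If every event falls in Cycle 1, both windows contain it and the gap is zero.

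**What the added measures do.** With r = 1 the daily hazard is 0.3567/211 = 0.00169.

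- *Onset by Day 42:* 1 − exp(−42 × 0.00169) = 6.9% in both groups. Even a 1-dose patient's window can reach Day 85, so Day 42 is covered unless death or new therapy comes first.
- *Exposure-adjusted rate* (patients with a first event, divided by time to first event or end of window): 0.164/97.0 days and 0.300/177.5 days, both 0.169 per 100 patient-days.

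The rate is exact only under a constant hazard. With r = 3 it gives 0.2052/91.8 = 0.224 per 100 patient-days for the short group and 0.300/170.2 = 0.176 for the long group. It then over-corrects by about 27% (0.224/0.176), while the Day 42 percentage stays equal at 14.1%. This is the reason for showing both.

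**The case against.** The strongest reply is that these tables are descriptive, the study is not randomized, and nothing is tested. A reader also has more than the percentages: an event count in the overview, exposure by dose level, laboratory summaries by scheduled visit, and full listings. That is fair. The exposure table reveals unequal exposure, but it does not adjust for it, and columns by dose level invite comparison whether or not a test is run.

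A reader might infer that the crude tables could mislead the choice of MTD or recommended dose. The documents do not support that. The CRM uses DLTs and Grade 2 or higher toxicities; its DLT period is one cycle, and it also takes in DLTs through Cycle 3. For Part 2 cohorts, Protocol 8.3 says the steering committee decides "taking into account the limit on the overall number of patients as specified above and safety/efficacy data observed up to that decision point", but does not say that it works from the tables in SAP 4.8.2.1. How the committee views data is left to a separate DESC Plan.

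A reader might also infer that low doses will always look safer. That does not follow either. Toxicity ends treatment too, so a toxic dose can have the shorter window and still show the higher percentage, though one understated relative to its rate. Fewer visits after Cycle 2 would, if anything, reduce detection of late events in patients who stay on drug and so narrow the gap.

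Finally, sampling error is large. With about 10 patients per level or cohort, the exact 95% interval for 3 of 10 is 6.7% to 65.2%. This stands, and it limits what any added table can show. Pooling dose levels would reduce that error but would not remove this bias.

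**Conclusion.** The point holds as a minor one. TEAE incidence by dose level is crude, the window varies with time on drug, and no planned TEAE analysis accounts for it. For events that can occur throughout treatment, the groups with shorter treatment will, other things equal, show lower percentages at the same hazard. This applies to dose levels and disease subtypes, and to Part 2 regimens if they are tabulated as groups, which the SAP does not state.

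Under the assumed hazards with the full 84-day tail, the all-2-dose versus all-7-dose contrast is about 5 to 14 points (30% against 25.4% to 16.4%), and wider if new therapy closes the short window early. That is an upper-end illustration, not an expected bias. The assumed mixtures give about 1 to 4 points. The true size cannot be computed from the documents. What is affected is the TEAE display and the reading of Part 2 tolerability.

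**What to change.** In SAP 4.8.2.1, keep the crude tables. Limit the additions to the overview categories (any TEAE; Grade 3 or higher; serious; leading to delay, reduction or interruption; leading to withdrawal) and the grouped TEAEs:

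1. Number and percentage of patients with onset in Cycles 1-2 (Day 1 to Day 42).
2. An exposure-adjusted incidence rate: patients with a first event per patient-time to first event or end of the TEAE window. Where numbers allow after pooling dose levels as SAP 4 permits, an alternative is the cumulative incidence of the first Grade 3 or higher TEAE over the whole TEAE window, with death as a competing event.

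State that differences in crude percentages are to be read together with these and the exposure table. State also that comparing regimens needs time after Cycle 3 or 4. Cycle 4 starts on Day 64 and Cycle 5 on Day 85, so a Day 42 table cannot separate regimens that are identical until then. For the same reason, comparisons should not rest on early windows alone, which would leave out later toxicity.

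The cost is SAP wording and a few tables from onset, dosing and subsequent-therapy dates already collected; conduct does not change. The limits to state are imprecision at about 10 patients per level, the constant-hazard assumption behind the rate, and possibly informative censoring at new therapy.

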7.3.2.2 Eliciting and Documenting Adverse Events

All AEs will be assessed from the time the patient signs the ICF until 84 days (12 weeks) after the last dose of study drug, or initiation of new anticancer treatment.

Any SAEs that occur > 84 days (12 weeks) after the last dose of study drug do not need to be reported unless the Investigator considers the event to be related to study drug.

At every study visit, patients will be asked a standard non-leading question to elicit any medically related changes in their well-being. They will also be asked if they have been hospitalized, had any accidents, used any new medications, or changed concomitant medication regimens (both prescription and over-the-counter medications).

In addition to patient observations, AEs will be documented from any data collected on the AE page of the eCRF (e.g., clinically significant changes in laboratory values, physical examination, ECG changes, etc.) or identified from review of other documents that are relevant to patient safety.

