8.6.2 Safety Analyses

8.6.2.1 Analyses of Adverse Events

An AE will be considered to be a TEAE if it begins or worsens on or after first dose date and before last dose date until 84 days (12 weeks). Planned summaries of TEAEs are detailed in the statistical analysis plan and will include:

- All TEAEs.
- All serious TEAEs.
- All treatment-related TEAEs.
- All treatment-related serious TEAEs.
- All TEAEs resulting in study drug discontinuation.
- All DLTs.
- Other AE analyses of interest will be specified in the SAP.

The incidence of deaths and the primary cause of death will be summarized.

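### The SAP leaves out the summary of treatment-related serious TEAEs that the protocol requires, and does not declare the change

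*SAP*

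**What the plan says.** Protocol 8.6.2.1 hands the detail to the SAP but fixes a minimum content: "Planned summaries of TEAEs are detailed in the statistical analysis plan and will include" all TEAEs, serious TEAEs, treatment-related TEAEs, treatment-related serious TEAEs, TEAEs resulting in study drug discontinuation, and DLTs. Further AE analyses may be added in the SAP. The fourth item reads "All treatment-related serious TEAEs".

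SAP 4.8.2.1 sets out the TEAE summaries for the safety analysis set at each dose level. The overview has the row "Related TEAE (including possibly related, probably related, or related)" and a separate row for serious TEAEs. The detailed tables include "All related TEAEs by primary SOC, PT and Maximal CTCAE grade (including possibly related, probably related, or related)" and "All Serious TEAEs by primary SOC, PT and Maximal CTCAE grade". No row or table crosses relationship with seriousness.

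SAP 3.3 declares one modification to the protocol's statistical section, the definition of the efficacy analysis set. After the tables, SAP 4.8.2.1 provides listings of all TEAEs, all SAEs and all non-TEAEs.

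**The concern.** The protocol asks for a specific output on the primary safety objective. The SAP, followed as written, would not produce it, and nothing shows that the omission was intended.

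The category matters in this trial. Protocol 7.3.2.5 treats every SAE at least possibly related to study drug as unexpected and reports it as a SUSAR. Such events would be expedited one by one during the study, yet the planned tables would not state, by dose level, how many patients had one.

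Separate related and serious tables do not replace the combined one. A patient may have a related event that is not serious and a serious event that is not related. The DLT tables in SAP 4.8.1 do not fill the gap: they cover Part 1 only, and a DLT is not defined by seriousness.

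**Working it through.** The plan states no figure on this point, so the check sets the two lists side by side and then asks whether the missing count can be recovered.

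**Step 1. Coverage of the summaries named in Protocol 8.6.2.1**

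| Protocol item | Planned SAP output |
|---|---|
| All TEAEs | Yes, 4.8.2.1 |
| Serious TEAEs | Yes, 4.8.2.1 |
| Treatment-related TEAEs | Yes, 4.8.2.1 |
| Treatment-related serious TEAEs | None |
| TEAEs leading to study drug discontinuation | Yes, 4.8.2.1 (treatment withdrawal) |
| DLTs | Yes, 4.8.1 (Part 1) |

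Coverage is 5 of 6.

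**Step 2. Can the count be derived from the planned tables?** Take two hypothetical patients at one dose level. Each has a single event, with the same preferred term and the same Grade 3.

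- Case 1: patient A's event is related and not serious; patient B's is serious and not related.
- Case 2: patient A's event is both related and serious; patient B's is neither.

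In both cases the tables show two patients with the term, one related at Grade 3 and one serious at Grade 3, and two events in total. The number of patients with a related serious TEAE is 0 in Case 1 and 1 in Case 2. The tables cannot tell the cases apart, even at preferred-term and grade level.

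**Step 3. Limits from the overview rows alone.** Let R be patients with any related TEAE, S patients with any serious TEAE, and n the group size. Patients carrying both flags number from max(0, R + S − n) to min(R, S). Those with a single event that is both related and serious number from 0 to min(R, S), because the two flags may come from different events. The documents give no expected rates, so the following rates are assumptions, applied to the roughly 60 patients of Part 2:

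- 80% related (48), 30% serious (18): both flags from max(0, 48 + 18 − 60) = 6 to 18; related serious event from 0 to 18.
- 60% related (36), 50% serious (30): both flags from max(0, 36 + 30 − 60) = 6 to 30; related serious event from 0 to 30.

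These are outer limits, not forecasts. The more detailed tables can narrow them, as Step 4 and the objection show.

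**Step 4. What can be read directly.** Grade 5 is death (Protocol 7.3.2.3), and an event that results in death is an SAE (Protocol 7.3.2.1). A Grade 5 entry in the related-by-grade table is therefore a related serious TEAE. Non-fatal related serious events remain undetermined.

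**Step 5. Would the listings do?** Seriousness and relationship are both recorded on the AE page (Protocol 7.3.2.3), so a hand count should be possible if the listings show both. It would not automatically agree with a programmed table. SAP 6.1.1 counts a TEAE with missing relationship as related in the frequency tables while leaving the data unimputed, so whoever counts from the listings must apply that rule too.

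**The case against.** The best defence is that little is lost. The analysis is descriptive, all SAEs are listed, and the SAP is to be read together with a protocol whose list has not been withdrawn. No dose decision or primary conclusion turns on this table. All of that stands, and it keeps the point modest. It does not turn a listing into the summary that the protocol names.

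The planned tables also say more than the overview limits suggest. Related Grade 5 events are visible. A preferred term that appears among serious but not among related TEAEs contributes nothing to the combined count. If the overview gives event numbers for each row, at least E_related + E_serious − E_total events are both: with assumed counts of 900, 150 and 1,000, that is 900 + 150 − 1,000 = 50. So it would be wrong to infer that drug-related serious toxicity is wholly untabulated, or that the count always lies anywhere from 0 to min(R, S). These devices narrow the range in some data sets. They do not yield patients per dose level in general, as the two-patient example shows.

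A reader might also infer a second defect from Protocol 7.3.2.2, under which SAEs more than 84 days after the last dose "do not need to be reported unless the Investigator considers the event to be related to study drug". SAP 4.8.2.1 says that events beyond the window "will not be included in TEAE displays, but will be listed as non-TEAEs". The documents do not support calling this an error:

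- The window is the protocol's own. Protocol 8.6.2.1 defines a TEAE as beginning or worsening "on or after first dose date and before last dose date until 84 days (12 weeks)", so the required summary would itself leave out later events.
- The SAP's further cut at new anticancer therapy matches the AE collection period in Protocol 7.3.2.2.
- Late SAEs are listed, and the deaths table in SAP 4.8.2.2 has no 84-day limit for deaths during the study, so a fatal late event is counted there as a death.
- After 84 days only SAEs judged related must be reported, and patients who have progressed or started new treatment are followed by telephone about every 12 weeks (Protocol 5.1.6). An incidence by dose from such selective reporting could mislead, so a listing is a defensible choice.

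**Conclusion.** The point holds for the missing summary. One of six summaries named in Protocol 8.6.2.1 has no counterpart in the SAP, and SAP 3.3 does not declare the change. Apart from related Grade 5 events, patients per dose level with a treatment-related serious TEAE cannot in general be read from the planned tables.

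The size in patients cannot be stated, because the documents give no expected rates of related or serious events. The conclusion does not rest on the assumed rates above. It rests on comparing the two lists, and on reading the list in SAP 4.8.2.1 as the set of summaries that will be programmed. This is a gap in tabulation and not in data collection: worth correcting because it concerns a primary objective, but not a threat to the trial's conclusions. The treatment of related SAEs after 84 days is not an error in the plan.

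**What to change.** In SAP 4.8.2.1:

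- add a row for treatment-related serious TEAEs to the overview;
- add a table of treatment-related serious TEAEs by SOC, PT and maximal CTCAE grade, by dose level;
- state that the missing-relationship rule in SAP 6.1.1 applies to both.

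If the sponsor did mean to drop the summary, SAP 3.3 should say so and give the reason.

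The cost is one more row and one more table, from data already collected. The TEAE definition, the design and the data collection do not change. A separate count of related SAEs after 84 days, with time since last dose, is optional. If it is added, it should be kept apart from the TEAE tables, with a note that reporting in that period depends on the Investigator's causality judgement.
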